5.2 Definition of Dose Limiting Toxicity

Toxicity will be graded using CTCAE version 4.0, with dose limiting toxicities being assessed during the first 28 days of treatment (cycle 1). Any dose limiting toxicity must be a toxicity that is considered related to study drug. Patients is considered evaluable for DLT assessment if < 7 days of full dose (according the specific dose level) treatment have been omitted. If at any day the treatment will not be assumed at full dose, it will be considered as omitted.

Dose limiting toxicity is defined as follows:

Haematologic:

- Absolute neutrophil count (ANC) $< 0.5 \times 10^9/L$
- Febrile Neutropenia (ANC $<1.0 \times 10^9$ /L, fever $\ge 38.5^\circ$ C)
- Platelets $<25 \times 10^9/L$
- Bleeding felt to be due to thrombocytopenia

Non-Haematologic:

- Diarrhea ≥ Grade 3 despite optimal loperamide use.
- Rash \geq Grade 3 or grade 2 if medically concerning or unacceptable to the patient.
- Other grade >3 effects thought to be treatment related.
- Missing >14 days of treatment for toxicity reasons.

Ocular Toxicity

Any occurrence of ocular toxicity that is greater than grade 1, including but not limited to retinopathy is considered to be a dose-limiting toxicity and the patient must discontinue the study medications.

Any Toxicity

Patients experiencing adverse events \geq grade 2 that do not recover within 2 weeks, despite optimal supportive management and treatment interruption.

Management and dose modifications associated with the above adverse events are outlined in Section 7.

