13.2.1 Patient Replacement

If a patient is withdrawn from the study prior to completing 28 days of therapy without experiencing a DLT prior to withdrawal, an additional patient may be added to that dose level. Patients missing 7 or more days due to toxicity will not be replaced since these patients will be considered to have experienced a dose limiting toxicity.

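### Sections 5.2 and 13.2.1 classify a patient who misses 7 to 14 days of cycle 1 for toxicity in opposite ways, which can reverse the dose decision

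*Protocol*

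**What the plan says.** Protocol Section 5.2 limits the DLT window to the first 28 days and sets evaluability: "Patients is considered evaluable for DLT assessment if < 7 days of full dose (according the specific dose level) treatment have been omitted". It counts reduced-dose days as well: "If at any day the treatment will not be assumed at full dose, it will be considered as omitted". Its only DLT criterion based on missed treatment alone is "Missing >14 days of treatment for toxicity reasons".

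Protocol Section 13.2.1 says that those "missing 7 or more days due to toxicity will not be replaced since these patients will be considered to have experienced a dose limiting toxicity". Its replacement rule covers patients withdrawn before completing 28 days "without experiencing a DLT prior to withdrawal, an additional patient may be added to that dose level".

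Section 13.1.1 refers to 5.2 for the definition of DLT, but no sentence gives either section precedence. Section 6 holds drug for several grade 2 and grade 3 toxicities and takes a patient off therapy only when the delay exceeds two weeks. The table in 5.3.1, the MTD definition in 5.3.2 and the accrual rule in 13.1 all turn on whether a dose level has at least two DLTs.

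**The concern.** A patient who misses between 7 and 14 days for toxicity, and meets no other criterion in 5.2, falls between the two sections. Section 13.2.1 adds this patient to the DLT count. Section 5.2 gives no DLT and treats the patient as not evaluable. Because Section 6 allows holds of up to two weeks, following the protocol as written can produce such a patient.

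At stake is the primary endpoint. Setting patients aside because of toxicity lowers the apparent DLT rate, so escalation, or an RP2D, could follow at a level that the other section would declare too toxic.

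A second, smaller gap lies within 5.2. Its evaluability sentence makes no explicit exception for a patient who has had a DLT. Read literally, it conflicts with the criterion of more than 14 missed days, since anyone meeting that criterion has omitted at least 7. It also conflicts with DLTs that end treatment with 7 or more days of cycle 1 remaining, such as ocular toxicity above grade 1, which "is considered to be a dose-limiting toxicity and the patient must discontinue the study medications".

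**Working it through.** The protocol states no DLT rate or operating characteristic for phase I, so there is no figure to reproduce. The check sets the two rules side by side, follows one cohort through the table, and then illustrates the size.

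**Classification, for a patient meeting no other DLT criterion**

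| Days missed for toxicity in cycle 1 | Section 5.2 | Section 13.2.1 |
|---|---|---|
| fewer than 7 | evaluable, no DLT | no DLT |
| 7 to 14 | not evaluable, no DLT | DLT, not replaced |
| more than 14 | DLT, but literally not evaluable | DLT, not replaced |

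The middle row is the contradiction.

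**One cohort, two decisions.** Six patients are treated at a level: one has an undisputed DLT, one misses 8 days for toxicity with no other criterion met, and four are clean.

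- Under 13.2.1: 2 DLTs in 6. This meets the MTD definition in 5.3.2, and the 5.3.1 table gives n - 1.
- Under 5.2: 1 DLT in 5 evaluable. If one clean patient is added to reach six evaluable, the count is 1 in 6 and the table gives n + 1, or RP2D at the top level.

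**Size under assumed rates.** Let d be the probability of a DLT on another criterion, and q the probability of missing 7 to 14 days for toxicity with no other DLT. Neither is in the protocol; both are assumptions.

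- Under 13.2.1 the DLT probability per evaluable patient is p = d + q.
- Under 5.2, if non-evaluable patients are replaced, p = d / (1 - q).
- P(at least 2 of 6) = 1 - (1 - p)^6 - 6p(1 - p)^5.

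With d = 0.10:

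| q | p, 13.2.1 | P(at least 2/6) | p, 5.2 with replacement | P(at least 2/6) |
|---|---|---|---|---|
| 0.10 | 0.20 | 0.345 | 0.10/0.90 = 0.111 | 0.137 |
| 0.20 | 0.30 | 0.580 | 0.10/0.80 = 0.125 | 0.167 |
| 0.30 | 0.40 | 0.767 | 0.10/0.70 = 0.143 | 0.207 |

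For q = 0.20 under 13.2.1: 1 - 0.70^6 - 6(0.30)(0.70^5) = 1 - 0.118 - 0.303 = 0.580 before rounding of the terms.

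Over a wider grid, d from 0.10 to 0.25 and q from 0.05 to 0.20, the gap between the readings runs from 0.08 (d = 0.25, q = 0.05: 0.580 against 0.497) to 0.41 (d = 0.10, q = 0.20: 0.580 against 0.167).

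**Sensitivity to always observing six.** Below the top level the table escalates after no DLTs in three, four or five fully observed patients. On a path of three patients, then six if one has a DLT, P(too toxic) = 1 - [(1 - p)^3 + 3p(1 - p)^2 (1 - p)^3].

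- p = 0.30: 1 - (0.343 + 0.441 x 0.343) = 0.51.
- p = 0.125: 1 - (0.670 + 0.287 x 0.670) = 0.14.

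The direction is the same and the figures are a little lower than 0.58 and 0.17.

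**The case against.** The conflict between 7 days and more than 14 days is plain on the text. Four points can be made against reading more into it.

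**Patients with a DLT.** A reader might infer that 5.2 removes patients who stop because of a DLT. The protocol does not support that as its intent. The ocular rule declares a DLT and orders discontinuation in one sentence, which is hard to read as discarding the patient. Section 5.3.1 bases decisions on the patients enrolled and how many of them had DLTs, with no evaluability filter. Section 13.2.1 allows an added patient only where no DLT preceded withdrawal. Also, 5.2 says evaluable if, not only if. This objection stands: the missing exception is a drafting gap to close, not a rule that discards DLTs.

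**Other criteria.** A patient missing 7 to 14 days may meet another 5.2 criterion, such as grade 3 rash, and is then a DLT under both sections. This stands and limits the contradiction to patients with no other qualifying event.

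**Replacement.** Section 5.2 contains no replacement rule. Section 13.2.1 replaces only withdrawn patients without a DLT, and expressly not those missing 7 or more days for toxicity. Adding a patient under the 5.2 reading is therefore an inference from the provision in 13.1 for up to six evaluable patients per level. This stands as a caveat on the figures. Without an added patient, the cohort above still reads 1 of 5 under one section and 2 of 6 under the other.

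**Figures.** A reader might take the probabilities as the design's operating characteristics. They are not: the rates are assumed and six patients are not always observed.

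**Conclusion.** The contradiction holds and needs correcting, because it concerns the count that determines the primary endpoint. For a patient who misses 7 to 14 days of cycle 1 for toxicity and meets no other criterion, the protocol gives two incompatible classifications and no order of precedence. One such patient is enough to reverse a decision. The MTD changes only if such patients occur and move the count across two.

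The illustrated size, 0.35 to 0.77 against 0.14 to 0.21 for declaring a level too toxic, rests on three assumptions: 10% other DLTs, 10% to 30% gaps of 7 to 14 days, and six evaluable patients with replacement of the non-evaluable. The direction does not depend on the particular rates: whenever such gaps occur, the 5.2 reading gives the lower apparent DLT rate.

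The absence of an exception for DLT patients in 5.2 is a secondary point that calls for clarifying wording only.

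**What to change.** - Reconcile 5.2 and 13.2.1 to one missed-days rule and use it in both sections. The clinical team chooses the threshold; no view is taken here on which is right. The rule should say whether reduced-dose days count, since 5.2 counts them as omitted and 13.2.1 speaks only of missing days.
- State in 5.2 that any patient with a DLT is evaluable however many days were omitted, and that a patient without a DLT is evaluable only if fewer than 7 days were omitted.
- If the chosen threshold leaves patients with 7 or more toxicity-related omitted days who are not DLTs, state how they enter the numerator and denominator, so that they are neither silently dropped and replaced nor counted as clean.

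The last item matters. If the threshold of more than 14 days were kept and these patients counted as clean, then at d = 0.10 the chance of at least 2 of 6 would be 1 - 0.90^6 - 6(0.10)(0.90^5) = 0.114. That is below the 0.167 under the present 5.2 reading with replacement at q = 0.20.

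The cost is a change of protocol wording. Whether escalation becomes more conservative depends on the threshold chosen and on how any remaining patients are counted.

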7.6 Follow-Up of AEs and SAEs

SAEs and AEs should be followed for 12 weeks after the last dosing of study drug/biologic or until they are resolved (return to normal or baseline values), stabilized, improve to Grade 1, or the patient is lost to follow-up and cannot be contacted. Additional investigations (*e.g.*, laboratory tests, diagnostic procedures, or consultation with other healthcare professionals) may be required to completely investigate the nature and/or causality of an AE or SAE. If the patient dies during the study or within 12 weeks following the last dose of study medication, any postmortem findings (including histopathology) should be provided to the Sponsor. CRF data should be updated with any new information as appropriate.

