13. STATISTICAL CONSIDERATIONS

13.1 Study Design/Endpoints

The rate of subject entry and escalation to the next dose level will depend upon assessment of the safety profile of patients entered at the previous dose level. Toxicity will be evaluated according to the NCI Common Terminology Criteria for Adverse Events (CTCAE), Version 4.0.

Up to six evaluable patients will be treated at a given dose level combination and observed for at least 4 weeks from start of treatment to assess toxicity for purposes of determining dose limiting toxicities (DLTs). When exactly 6 patients have been enrolled on a given dose level and it is unknown whether the MTD has been exceeded or not, accrual will be suspended until enough toxicity data are available to decide (i.e. to determine if the dose level has at least 2 DLTs versus less than 2).

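### Two DLT criteria need about two weeks to complete, but the protocol does not say how a patient whose event is still open at day 28 is counted in the escalation table

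*Protocol*

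**What the plan says.** Section 5.2 of the protocol has "dose limiting toxicities being assessed during the first 28 days of treatment (cycle 1"). Two criteria in its DLT list depend on duration:

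- Under the any-toxicity item, a DLT is an adverse event of grade 2 or higher "that do not recover within 2 weeks, despite optimal supportive management and treatment interruption". The start of the two-week clock (onset or interruption) is not given.
- Under the non-haematologic items: "Missing >14 days of treatment for toxicity reasons".

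The same section opens its evaluability rule with "Patients is considered evaluable for DLT assessment if < 7 days of full dose" treatment omitted, so 7 or more omitted days make a patient non-evaluable.

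Section 13.2.1 takes a different line on missed days: "Patients missing 7 or more days due to toxicity will not be replaced", because they count as having had a DLT.

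Section 13.1 has patients "observed for at least 4 weeks from start of treatment to assess toxicity". When exactly six are enrolled at a level and the MTD question is open, "accrual will be suspended until enough toxicity data are available to decide". Section 7.6 adds that "SAEs and AEs should be followed for 12 weeks after the last dosing of study drug/biologic or until they are resolved" or otherwise settled.

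The Section 5.3.1 table assigns the next patient's dose level from the numbers with a DLT, without a DLT, and with data pending.

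**The concern.** A criterion that takes two weeks to complete sits inside a four-week window, and the protocol does not say which end of the event must fall in that window. If completion must, a persistent toxicity that begins in the second half of cycle 1 does not meet the criterion by day 28. If onset is enough, it does meet it, but only after day 28, and then the table needs to know that the patient is still pending. Neither rule is written down.

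The table acts on this classification. With 3, 4 or 5 enrolled, no DLTs and none pending, it moves to the next level (below the maximum level). With one of those patients pending, it stays at the current level. One patient's status can therefore decide whether the dose goes up. The DLT count sets the MTD and the recommended phase II dose, which is the primary endpoint, and patients treated at that dose also count towards stage 1 of phase II.

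The two criteria are not marginal. As printed, the catch-all for other related effects is set above grade 3, so a grade 3 event outside the named categories becomes a DLT mainly through persistence or missed days.

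**Working it through.** The protocol gives no operating characteristics for this rule, so there is no figure to reproduce. The check is a day count, a comparison of the sections, and an illustration under assumed rates.

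**1. Latest qualifying onset if completion by day 28 is required.** For onset on day d, the two weeks end on d+13 (onset day counted as day 1), d+14 (14 days elapsed) or d+15 (still open the day after). Setting each to at most 28 gives:

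| Convention | Latest onset | Onset days that cannot qualify |
|---|---|---|
| d+13 | day 15 | 13/28 = 46% |
| d+14 | day 14 | 14/28 = 50% |
| d+15 | day 13 | 15/28 = 54% |

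**2. Missed days.** A hold that starts on day s and continues gives 29 − s missed days by day 28. More than 14 requires s ≤ 14. Seven or more requires s ≤ 22.

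**3. Status at day 28 of a continuing hold, by section.**

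| Hold starts | Missed by day 28 | Section 5.2, read literally | Section 13.2.1 |
|---|---|---|---|
| Days 1–14 | 28 to 15 | DLT | DLT |
| Days 15–22 | 14 to 7 | No DLT by missed days; not evaluable | DLT |
| Days 23–28 | 6 to 1 | Evaluable, no DLT by missed days | No DLT |

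The last row is 6/28 = 21% of start days. For example, with a hold from day 24 the patient has 5 missed days at day 28 and counts as without DLT. The fifteenth missed day falls on day 38. By then the event meets the protocol's own DLT wording and the Section 6 rule for leaving protocol therapy after a delay of more than two weeks.

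**4. Illustration.** Assumptions, none from the protocol: each patient has a 10% chance of some other DLT and, independently, a chance q of a persistent event of grade 2 or higher; onset is uniform over days 1–28; the hold starts at onset. Let f be the share of persistent events that are counted:

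- counted DLT rate: p = 1 − 0.9 × (1 − q·f)
- level not exceeded at six patients: P(at most 1 of 6) = (1−p)^6 + 6p(1−p)^5
- escalation at three patients: P(0 of 3) = (1−p)^3

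Three values of f are used: f = 1 (all followed and counted), f = 22/28 (only days 23–28 lost, with Section 13.2.1 applied), and f = 14/28 (days 15–28 lost, the 14-days-elapsed convention).

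| q | p: f = 1, 22/28, 14/28 | P(at most 1 of 6) | P(0 of 3) |
|---|---|---|---|
| 10% | 0.190, 0.171, 0.145 | 0.68, 0.73, 0.79 | 0.53, 0.57, 0.63 |
| 20% | 0.280, 0.241, 0.190 | 0.46, 0.55, 0.68 | 0.37, 0.44, 0.53 |
| 30% | 0.370, 0.312, 0.235 | 0.28, 0.39, 0.57 | 0.25, 0.33, 0.45 |

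For q = 20% and three patients: 0.72³ = 0.37, 0.759³ = 0.44, 0.81³ = 0.53.

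**5. Longest wait if onset counts.** An event starting on day 28 is settled at about 28 + 14 = day 42, and no onset day is lost.

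**The case against.** The strongest reply is that completion by day 28 is only one reading. Section 13.1 sets four weeks as a minimum, the table has a column for pending data into which an open event fits naturally, and Section 7.6 ensures that the outcome is recorded. This stands. A reader might infer that half the window cannot produce this DLT, but that needs a hard stop at day 28, which the protocol does not impose.

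Second, the criterion itself presupposes interruption, and Section 6 holds both drugs at grade 2 for most toxicities. A hold that starts on days 15–22 and continues reaches 7 missed days by day 28. The patient is then a DLT under Section 13.2.1 or non-evaluable under Section 5.2, and under neither is she simply without DLT. This also stands, and it narrows the clear gap to days 23–28. It does so only by exposing a conflict between the two sections.

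Third, severe late events such as neutrophils below 0.5, platelets below 25, or diarrhoea of grade 3 or higher despite loperamide count at once. That is correct; only the duration-based criteria are affected.

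A reader might also infer from the 40-day half-life of hydroxychloroquine in Section 2.2.2 that late events are the likelier ones. The protocol gives no onset-time data, so that is conjecture, and the illustration does not use it.

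What the reply does not supply is a rule. A minimum observation time does not classify an open event, adverse event follow-up does not feed the DLT count, and the accrual suspension is written for exactly six enrolled, not for three to five.

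**Conclusion.** The point holds as a gap and an inconsistency in the counting rule. It is not a demonstrated downward bias in the DLT count. Followed literally, the window and the table can escalate over an unresolved toxicity that later meets the protocol's own DLT definition, and two readers could classify the same patient differently.

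The size depends on the reading. Starts on days 23–28 (21% of the window) are caught by neither missed-dose rule by day 28. Starts on days 15–22 get conflicting classifications. The figure of about half (46–54%) applies only if completion by day 28 is required and Section 13.2.1 gives no rescue. If onset suffices and the outcome is followed, nothing is lost.

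The probabilities rest on assumed event rates and uniform onset. The lower set also assumes that holds start at onset and that Section 13.2.1 governs. The higher set is the upper end under the 14-days-elapsed convention. They show that the effect can matter, not how large it is in this trial. The point should be settled in the text before escalation decisions depend on it.

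**What to change.** Reconcile Sections 5.2, 13.1 and 13.2.1 on three matters: whether onset or completion must fall within days 1–28, when the two-week clock starts, and how the 7-day and 14-day missed-dose rules and the evaluability rule fit together. Which missed-dose threshold applies is for the investigators to decide. The need is for one consistent statement.

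Then add to Section 5.3.1 that a patient with a potentially qualifying event or interruption that began in days 1–28 and is still open at day 28 is counted as data pending until it is settled, at the latest about day 42.

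This takes a few sentences and no new data, since adverse events are already followed beyond cycle 1. The cost is up to about two more weeks of pending status for the few patients concerned. During that time the table keeps enrolment at the current level when three to five are enrolled, and may hold accrual at six.

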5.3 Rolling Six Design

The rolling six design allows for accrual of 2 to 6 patients concurrently on the same dose level.

The dose of hydroxychloroquine will be escalated in fixed increments according to the dose escalation scheme outlined below.

Dose level	Dose of itraconazole (total daily dose)	Dose of HYDROXYCHLOROQUINE (total daily dose)	Minimum number of patients	Maximum number of patients
	300 mg BID	200 mg OD (200 mg total)		6
-1	(600 mg total)	200 mg 02 (200 mg total)		C
1	300 mg BID	200 mg BID (400 mg total)	2	6
(starting)	(600 mg total)		2	
2	300 mg BID	400 mg BID (800 mg total)	2	6
2	(600 mg total)		2	
3	300 mg BID	600 mg BID (1200 mg total)	2	6
3	(600 mg total)		2	

5.3.1 Specific Dose Escalation and De-Escalation Rules for this Trial

- Starting dose level is 1.
- The dose level -1 block will be used if and only if dose level 1 is too toxic (i.e. if dose level 1 is above the MTD).

Determination of which dose level to enroll a patient into will be made according to the table below (adapted from [47]). The decision is based on the number of patients currently enrolled on a specific dose level, how many of them experienced DLTs, and how many patients are still pending data on DLTs experienced.

		DLT Data		Enrolling Do	ose Level*
# Currently Enrolled	# Patients with DLTs	# of Patients without DLTs	# of Patients w/Data Pending	When n is lower than Trial Maximum	When n is at Trial Maximum
2	0, 1	Any	Any	n	
2	2	0	0	n - 1	
3	0	0, 1, 2	3, 2, 1	n	
3	0	3	0	n + 1	
3	1	0. 1	2, 1	n	
3	1	2	0	n	
3	≥ 2	Any	Any	n - 1	
4	0	0, 1, 2	4, 3, 2	n	n
4	0	3	1	n	n
4	0	4	0	n + 1	n
4	1	0, 1	3, 2	n	n
4	1	2	1	n	n
4	1	3	0	n	n
4	≥ 2	Any	Any	n - 1	n - 1
5	0	0, 1, 2	5, 4, 3	n	n
5	0	3, 4	2, 1	n	n
5	0	5	0	n + 1	n
5	1	0, 1	4, 3	n	n
5	1	2	2	n	n
5	1	3, 4	1, 0	n	n
5	≥ 2	Any	Any	n - 1	n - 1
6	0	0, 1, 2	6, 5, 4	Accrual hold	Accrual hold
6	0	3, 4	3, 2	Accrual hold	Accrual hold
6	0	5, 6	1, 0	n + 1	RP2D
6	1	0, 1	5, 4	Accrual hold	Accrual hold
6	1	2	3	Accrual hold	Accrual hold
6	1	3,4	2, 1	Accrual hold	Accrual hold
6	1	5	0	n + 1	RP2D
6	≥ 2	Any	Any	n - 1	n - 1

Abbreviations: DLT - dose limiting toxicity; RP2D - recommended phase 2 dose

 $[\]ast$ n is the current dose level of patients enrolled; n + 1 and n - 1 represent dose level escalation and deescalation, respectively.

5.3.2 Recommended Phase II Dose

The MTD is defined as the dose at which $\geq 2/3$ or $\geq 2/6$ patients experience dose limiting toxicity.

The dose one level below the MTD will be considered the RP2D. If the maximum tolerated dose is not reached on the phase I trial, the maximum administered dose will be the RP2D, which will be used for the purposes of the phase 2 cohort.

Up to a total of 6 patients may be treated at the recommended dose to assure information on the safety profile at that dose is complete.

